The PI developed a web-based intervention (UV4.me) that was found to significantly decrease UV exposure and increase skin protection behaviors among young adults in a randomized controlled trial (RCT) of nearly 1000 participants recruited from a consumer research panel. The intervention (UV4.me) is individually-tailored, interactive, and multimedia in nature, and based on the Integrative Model of Behavioral Prediction. Similar to other online trials, 73% of eligible individuals completed the baseline questionnaire, 70% who were randomized to the intervention accessed it, and 68% accessed it and completed at least one module. However, we have an opportunity to increase the engagement, implementation, and ultimately, the impact of UV4.me. We will do this by adding several key interactive features/strategies suggested by participants, our data, and supported by the literature (i.e., by creating a mobile version, adding incentives embedded in the intervention, a behavior tracking and feedback feature, peer interaction component, and ongoing news updates). This Hybrid Type 2 dissemination-effectiveness project's purpose is to implement the enhanced intervention (UV4.me2) with adults aged 18-25 years at moderate to high risk of developing skin cancer and evaluate the intervention's effectiveness in a sample recruited online through national dissemination to the general population. This project will use the RE-AIM framework to determine the reach, effectiveness, implementation, maintenance, and cost of UV4.me2.

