2.1 Primary Aims

Primary Aim 1. To enhance and determine intervention reach (i.e., enrollment, representativeness).

Primary Aim 2. To determine the effectiveness of the enhanced intervention.

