We developed a web intervention that included many of the components found in successful internet interventions. We found significantly improved skin cancer risk behaviors among young adults in an RCT that enrolled almost 1000 participants from a consumer research panel 59. To our knowledge, this is the only empirically-tested internet intervention focused on skin cancer risk behaviors targeting young adults. The intervention (UV4.me) is individually-tailored, interactive, and multimedia based on Ritterband and colleagues' 60 model for online behavior change interventions and the Integrative Model of Behavioral Prediction 61, which includes background variables such as demographics; cognitive variables such as beliefs, attitudes, norms, and self-efficacy; intentions; and behavior. We also emphasized appearance concerns, which is a major factor associated with young adult tanning 62-64.

In addition to successful outcomes, approximately two thirds of eligible participants enrolled in the study and completed the baseline survey, two thirds randomized to UV4.me accessed the intervention, and two thirds completed the 3-month follow-up. Yet, we still have an opportunity to increase UV4.me implementation and impact. We propose to do this by enhancing recruitment and enrollment strategies as well as incorporating additional interactive features into the intervention (i.e., creating a mobile version, embedding incentives into the intervention, adding a behavior tracking and feedback feature, peer interaction component, and ongoing news updates). Features/strategies were chosen based on participant feedback, our data (e.g., attempted use of mobile devices), and reviews/models of effective e-Health interventions including for tobacco cessation, physical activity, weight loss, and nutrition 60,65-68 and online implementation strategies 69-72. Several enhancements are expected to improve reach, implementation, and behavioral outcomes simultaneously.

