13.0 Statistical Analysis

13.1 Statistical Analyses for Primary Aims

Reach. We will use a one-sample test of a binomial proportion (two-sided, α =0.05) to determine whether the fraction of eligible subjects who enroll and complete the baseline is higher in this project than the prior study. Assuming that 70% of eligible subjects enroll and complete the baseline, we will need access to 2,143 (i.e., 1500/0.70) eligible subjects. Given this sample size, we will be able to detect an increased enrollment and baseline completion proportion with at least 98% power if the true proportion is 70%. Demographic data from enrolled participants will be compared to census data using chi-square goodness of fit tests (two-sided, α =0.05). We will also use the same methods to compare enrollment rates and representativeness separately by recruitment source (i.e., skin protection organizations, Google Adwords, paid Facebook ads, consumer research panel, word of mouth [e.g., unpaid Facebook page, earned media]).

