16.0 Quality Assurance Procedures and Participant Confidentiality

Information about study subjects will be kept confidential and managed according to the requirements of the Health Insurance Portability and Accountability Act of 1996 (HIPAA). Those regulations required a signed subject authorization informing the subject of the following: The protected health information (PHI) that will be collected from patient; who will have access to that information and why; who will use or disclose that information; the rights of a research subject to revoke their authorization or use their PHI. In the event that a participant revokes authorization to collect or use PHI, the investigator, by regulation, retains the ability to use all information prior to the revocation of subject authorization. Data collected through the Internet will be obtained through secured means and stored on password protected servers as described above. These data will be labeled with participant numbers only. All data on servers are password-protected and limited to authorized research personnel.

We will employ several strategies to minimize repeat enrollment and enhance data quality, as recommended by the literature 98,143-151. These will include 1) verification of enrollment of participants with non-unique Personal Health Information (e.g., IP [Internet Protocol] address, email address, telephone number, name), and 2) separate analysis of data that indicates patterned (e.g.,

responding "always" to several items in a row), careless (e.g., too quick, illogical, gibberish, profane), or potentially fraudulent responding. We will create a summary index of such variables and conduct a latent class analysis to make a final decision about data inclusion/exclusion 146,152 as we did for the original UV4.me. The consumer research panel also employs such strategies to ensure data accuracy from its panel members such as providing researchers with panel entry data such as demographics, geolocation, socioeconomics, and health/behaviors to confirm eligibility and response consistency. By employing these procedures, we believe that we will be able to keep poor quality questionnaires relatively low at 5% of initially eligible participants, which is consistent with typical inattention 144,147,149. Thus, we will plan to over-recruit by as much as 5% until we have the required number of quality baseline surveys from unique eligible participants.

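### The Reach test claims at least 98% power without stating the prior-study rate it tests against, and the document describes that rate in two ways that do not agree

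*Combined protocol and SAP*

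**What the plan says.** Section 13.1 (Reach) specifies a one-sample test of a binomial proportion, two-sided at 5%. It asks whether the fraction of eligible people who enrol and complete baseline is higher than in the prior study. It assumes 70%, so 1,500 participants require 2,143 eligible people, and it concludes that "we will be able to detect an increased enrollment and baseline completion proportion with at least 98% power if the true proportion is 70" per cent. No prior-study proportion appears in the section.

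Two other places describe the prior rate:

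- Section 3.0: "approximately two thirds of eligible participants enrolled in the study and completed the baseline survey".
- Section 1.0: "73% of eligible individuals completed the baseline questionnaire".

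Hypothesis 1 (section 2.3) expects a higher enrolment rate than in the original UV4.me study, and enrolment is the first element of Primary Aim 1 (section 2.1).

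**The concern.** A one-sample test is not fully specified until its null value is given, and its power cannot be checked without that value. The efficacy part of section 13.1 does state the prior-study means and standard deviations behind its power. The Reach part gives no such input.

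The two descriptions elsewhere do not settle the matter. The phrase in section 3.0 is loose: the same sentence says that "two thirds randomized to UV4.me accessed the intervention", a rate that section 1.0 reports as "70% who were randomized to the intervention accessed it". If section 1.0's 73% measures the same thing as the Reach endpoint, the assumed 70% lies below the benchmark it is meant to exceed.

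At stake is how a primary-aim result will be read. An observed 70% would usually count as an increase against 66% and as a shortfall against 73%, and the plan does not fix in advance which benchmark applies.

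**Working it through.** **Inputs.** From section 13.1: n = 1,500/0.70 = 2,142.9, rounded to 2,143, which reproduces the plan's figure; true rate p1 = 0.70; two-sided α = 0.05, z = 1.96. The null p0 is not stated, so it is varied.

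**Formula (normal approximation).** Power = Φ{[(p1 − p0) − 1.96·√(p0(1−p0)/n)] / √(p1(1−p1)/n)}, with √(0.70 × 0.30/2,143) = 0.00990.

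**Can the plan's 98% be reproduced?**

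- p0 = 0.66: √(0.66 × 0.34/2,143) = 0.01023, so (0.0400 − 0.0201)/0.00990 = 2.01 and power is 97.8%.
- p0 = 2/3: √(0.2222/2,143) = 0.01018, so (0.0333 − 0.0200)/0.00990 = 1.35 and power is 91.2%.
- Solving for power of exactly 98% gives p0 = 0.6596.

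**Exact binomial check** (score-test rejection region, n = 2,143, true rate 70%):

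| Null p0 | Smallest count for a significant increase | Power |
|---|---|---|
| 65% | 1,437 | 99.9% |
| 66% | 1,458 | 97.7% |
| two thirds | 1,472 | 91.1% |
| 67% | 1,479 | 84.6% |
| 68% | 1,500 | 51.3% |

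So the claim needs a null of about 66% or lower. Going from 66% to 67% costs about 13 percentage points of power.

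**If the null were 73%.** A true 70% is then on the wrong side. The chance of a significant increase is below 0.00001, and the chance of a significant decrease is about 87%. The true rate needed for 80% power is 75.7%, against 68.8% for a null of 66% and 69.5% for a null of two thirds.

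**The prior rate as an estimate.** The one-sample test treats the prior rate as known. Section 1.0 says the prior trial had "nearly 1000 participants recruited from a consumer research panel". Its number of eligible people is not given. Taking up to 1,000 enrolled as an assumption, 1,000/0.73 = 1,370 and 1,000/(2/3) = 1,500, so m is taken as 1,300 to 1,500.

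- One-sample 95% half-width: 1.96 × 0.00990 = 1.9 points.
- Two-sample half-width: 1.96·√(0.21/2,143 + p0(1−p0)/m) = 3.1 to 3.2 points, for p0 of 66% or two thirds.
- Two-sample power at a true 70% (pooled null variance): 69% to 72% if the prior rate is 66%, and 53% to 57% if it is two thirds.
- Suppose the two studies have the same true rate and the prior estimate is used as a fixed null. The actual two-sided error is then 2Φ(−1.96·√[m/(m + n)]). For m = 1,300 this is 2Φ(−1.20) = 23%; for m = 1,500 it is 2Φ(−1.26) = 21%. The nominal level is 5%.

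**The case against.** The strongest reply is that no error has been shown. A fair reading of about two thirds is 66%, which gives 97.7% to 98.1% depending on the two-sided variant used. If recruitment stops at exactly 1,500 enrolled instead of at 2,143 eligible, power at 66% is 98.1%, which meets the claim literally. This stands: a reader might infer that the 98% is wrong, and the documents do not support that. What remains is that the input is missing and the result is very sensitive to it. At exactly two thirds the stop-at-1,500 variant still gives only 91.9%.

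The second reply is that 73% was never the intended null. Section 13.1 calls 70% an increase, and its endpoint matches the wording of section 3.0 more closely than that of section 1.0. This also stands. A reader might infer that the trial was planned around a decrease; that would hold only if 73% is the same measure and is the benchmark, and the plan's own wording weighs against it. The conflict between the two descriptions still needs resolving.

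Two further inferences should be resisted. Section 16.0 says the original study also used a data-quality screen ("as we did for the original UV4.me"), but nothing says that this explains the gap between the two rates. Nor does the plan claim 98% power for the comparisons by recruitment source; the figure is given for the overall test only.

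Finally, the prior rate is already fixed and the cited trial report may contain it. That limits the room for choosing a benchmark later, but it does not replace stating the value in the plan.

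**Conclusion.** The point holds as a specification gap with a conflicting benchmark. It is not a demonstrated miscalculation. At least 98% power requires a prior rate of about 66% or lower, and the document nowhere states such a value. Power is 97.7% at 66%, 91% at exactly two thirds and 85% at 67%. At 73%, the less likely null, 70% would contradict Hypothesis 1.

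These figures rest only on n = 2,143, a true rate of 70% and a two-sided 5% test. A separate weakness is that the one-sample test ignores the uncertainty in the prior rate. The size of that effect (a half-width of about 3.1 instead of 1.9 points, and a real error rate of about 21% to 23%) depends on the assumed 1,300 to 1,500 prior eligible people.

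The consequence is confined to the Reach aim. The 1,500 sample size and the efficacy comparisons, with their error rate and power, are unaffected.

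**What to change.** 1. Reconcile sections 1.0 and 3.0: say whether 73% and about two thirds count the same thing, and if not, define each.
2. State in section 13.1 the prior-study numerator, denominator and definition used as the benchmark.
3. Restate the power for that value: about 98% at 66%, or 91% at exactly two thirds. At 73%, a true rate of about 75.7% is needed for 80% power, and the 70% assumption would have to be revisited against Hypothesis 1.
4. Compare the two studies with a two-sample test and a 95% confidence interval for the difference, using the prior counts.

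Items 1 to 3 cost a few sentences and one recalculation, with no extra participants; the team ran the prior study and should hold the counts. Item 4 has a real downside. Under the assumed prior denominator the interval widens to about ±3.1 points, and power at a true 70% falls to about 69–72% (prior rate 66%) or 53–57% (two thirds). That lower power should be stated in the plan.

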RE-AIM Framework. One of the major problems with health behavior research is that many interventions that demonstrate initial effects are never tested in effectiveness or dissemination trials, nor are they distributed to populations who most need them, thus, having little impact on population health 34. To address these concerns, the RE-AIM Framework was developed by Glasgow and colleagues 35. "RE-AIM" refers to Reach, Effectiveness, Adoption, Implementation, and Maintenance. Reach refers to the number, proportion, and representativeness of individuals willing to participate in a given initiative, indicating potential generalizability 36. Effectiveness refers to the impact of an intervention on important outcomes, including potential negative effects, quality of life, and economic outcomes. Adoption refers to the absolute number, proportion, and representativeness of settings and intervention agents who are willing to initiate a program (not a main focus of the proposed project given the self-administered and automated intervention). Implementation refers to the individual's use of the intervention. Maintenance refers to the long-term effects of a program on outcomes. Although widely used since 1999, most reviews have found that the components of the RE-AIM framework are not assessed and/or reported comprehensively or well 37-41. Additionally, most dissemination and implementation (D&I) studies focus on dissemination of guidelines, policies, practices, or interventions to healthcare agencies or practitioners rather than D&I of online self-administered interventions directly to consumers. We selected the RE-AIM framework over many others because we believe it is the most appropriate to investigate the dissemination, implementation, and effectiveness of an innovative self-administered and automated online intervention. We could identify no relevant studies that addressed D&I issues related to self-administered materials online.

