2.3 Hypotheses

Hypothesis 1. We hypothesize that the study enrollment rate will be greater than in the original UV4.me efficacy study and that our sample will be representative of national demographics of young adults other than race/ethnicity (associated with skin cancer risk), indicating potential generalizability.

Hypothesis 2. We hypothesize that the UV4.me2 will be the most effective intervention, followed by UV4.me.

Hypothesis 3. We hypothesize that maintenance outcomes will be best in the UV4.me2 group, next best for UV4.me, and least for the e-pamphlet group.

Hypothesis 4. We hypothesize that greater intervention utilization (e.g., logins, module completion) and satisfaction will be associated with better behavioral outcomes

Hypothesis 5. We hypothesize that UV4.me2 and UV4.me will have higher incremental costs than the epamphlet. However, because UV4.me2 and UV4.me are also expected to result in better behavioral outcomes, we will assess cost-effectiveness to address whether these interventions are worth the additional costs.

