4.0 Study Design

4.1 Recruitment

A small number of human subjects will participate in acceptability testing (20-25 participants) and usability testing (12-15 participants). After acceptability and usability testing, a national sample of 1500 human subjects will be recruited to participate in the Randomized Control Trial (RCT). Therefore, we have a lower accrual goal of 1,532 and an upper accrual goal of 1,540.

Five types of online sources will be used to reach young adults: 1) national non-profit and for-profit skincare organizations (e.g., the Melanoma Research Foundation and Blue Lizard Sunscreen), 2) Google Adwords, 3) paid Facebook ads, 4) a consumer research panel, and 5) word of mouth (e.g., unpaid study Facebook page, earned social and traditional media [free publicity from a third party]). Google Adwords and Facebook are common online recruitment sources for young adults that can produce cost-effective, representative, and quality samples/data 87-95. Facebook is the largest social networking website and the second most popular website in the US after Google 96. Because some participants may know one another (e.g., from Facebook), we will inquire about/control for contamination between intervention conditions. Consumer research panels possess the qualities of Google Adwords and Facebook and can also produce guaranteed enrollment/data collection within a specified time-frame and budget 97-103, as occurred in the original UV4.me study. The team will refine web banner ads and create a Facebook study webpage to recruit individuals from the five online sources. Enrolled participants will be informed about the Facebook page, and non-enrolled individuals will be able to find the publicly available page organically by being referred by friends or searching Facebook or the web for related topics. To facilitate recruitment via Google and Facebook (also Bing and Yahoo), we will work with young adults and www.PatientRecruitmentOnline.com to help develop our keywords, ads, and recruitment plans. PatientRecruitmentOnline.com is made up of experts in online marketing specifically for health-related study recruitment. They will assist us in refining our keywords, ads, recruitment campaign, homepage, and enrollment process.

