4.4 Measures

4.4.1 Measures for Primary Aims

Screener. Participants will be screened with [name] 9-item Brief Skin Cancer Risk Assessment Tool (see Inclusion Criteria above) 104. Internal and test-retest reliability compare favorably to those reported in the literature for similar items/scales 104. Participants will be required to understand English and have access to the internet via any modality (e.g., computer, smartphone) at least weekly.

Demographics. Standard demographic items used by the census will assess: sex, age/birthdate, race/ethnicity, region of residence, education, income, and employment. We will include items on web use from the Health Information National Trends Survey 121, and will inquire about family history of skin cancer.

Social Desirability. Social Desirability will be assessed using the 4-item Brief Social Desirability Scale that has demonstrated adequate internal reliability and validity among young adults 122.

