Reach. We will assess eligibility and enrollment overall and by recruitment source (i.e., skin protection organizations, Google Adwords, Facebook ads, consumer research panel, word of mouth) over 12-18 months in order to assess reach/potential generalizability. Sources will be tracked by placing a unique identifying pixel in each of our authorized web ads so that we know when an individual referred from a pre-specified source accesses the study website. Additionally, we will query participants as to how they found out about the study to identify informal word of mouth diffusion (e.g., unpaid study Facebook page, earned media). The number of individuals who click on the web ads, access the study homepage, complete a screening form, are eligible/ineligible, and use the website without enrolling will be assessed. Organizational sources will be monitored and queried as to strategies (i.e., posting the study URL on their website, additional promotion) used to encourage individual participation. As we have previously, we will use Google Analytics to observe user characteristics and behavior in aggregate in terms of internet source including diffusion via word of mouth, geographic location, technology used (i.e., mobile or not), eligibility/enrollment rates, and so on. We will ask organizations to set up or allow us to set up a Google Analytics "goal" to assess such user characteristics and behavior in terms of individuals accessing the study ad from within the organization's website. We will also query organizations about their number of users/members and website views if they are monitoring these.

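### Hypothesis 1 predicts a demographically representative sample, but the only planned analysis is a chi-square test with that prediction as its null, which cannot in itself support it

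*Combined protocol and SAP*

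**What the plan says.** Section 2.1 states Primary Aim 1 as "To enhance and determine intervention reach (i.e., enrollment, representativeness", and the RE-AIM description in section 1.0 uses the same idea: "Reach refers to the number, proportion, and representativeness of individuals willing to participate in a given initiative". Section 2.3 turns it into a prediction, that "our sample will be representative of national demographics of young adults other than race/ethnicity".

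Section 13.1 (Reach) gives the analysis in one sentence: "Demographic data from enrolled participants will be compared to census data using chi-square goodness of fit tests", two-sided at alpha 0.05. It then adds: "We will also use the same methods to compare enrollment rates and representativeness separately by recruitment source".

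The variables are described in section 4.4.1: "Standard demographic items used by the census will assess: sex, age/birthdate, race/ethnicity, region of residence, education, income, and employment". The Reach paragraph of the same section says what is counted by source, "in order to assess reach/potential generalizability".

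None of these sections gives an estimate of the difference from the census, a confidence interval, or a criterion for calling the sample representative. The sample-size and power statement under Reach covers the enrollment rate only.

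**The concern.** A goodness-of-fit test asks whether the data are incompatible with a stated distribution. Here that distribution is the census, so the prediction in Hypothesis 1 is the null. Failing to reject is not in itself evidence that the null is true. Rejecting shows that some gap exists, without saying whether it is large enough to limit generalizability. For a given true gap, the result depends on the number enrolled, and nothing in the plan says how large a gap is acceptable.

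At stake is one of the two named components of a primary aim. If only the planned tests are reported, the reader learns whether each p-value crossed 0.05, but not how far the sample lies from the national population or whether Hypothesis 1 was borne out.

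**Working it through.** **The plan's own Reach figure.** 1500/0.70 = 2,142.9, rounded up to 2,143 eligible subjects, as stated in section 13.1. It concerns the enrollment rate. There is no corresponding figure for representativeness to reproduce.

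**Inputs.**
- n = 1,500 enrolled (section 4.1) and alpha = 0.05 two-sided (section 13.1).
- Assumptions, because the documents give no census shares: a binary trait with census share p = 0.50, and other splits where named.
- The census share is treated as known and the sample as binomial; normal approximation throughout.

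**Where significance begins.** SE = sqrt(p(1−p)/n) = sqrt(0.25/1500) = 1.29 points. The test is significant when the observed gap exceeds 1.96 × 1.29 = 2.53 points. At exactly that gap the 95% interval runs from 0.0 to 5.1 points.

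**How often a true gap d is rejected.** Non-central chi-square, 1 df, non-centrality n·d²/(p(1−p)):

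| True gap | Non-centrality | Rejected |
|---|---|---|
| 2 points | 1500 × 0.0004/0.25 = 2.4 | 34% |
| 3 points | 1500 × 0.0009/0.25 = 5.4 | 64% |
| 5 points | 1500 × 0.0025/0.25 = 15 | 97% |

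**What a non-significant result would bound.** The largest non-significant gap plus the interval half-width:
- 50% binary trait: 2.53 + 2.53 = 5.06 points (95% interval), or 2.53 + 2.12 = 4.65 points (90% interval).
- 10% binary trait: 1.52 + 1.52 = 3.04 points. Using the SE at the observed share instead gives about 3.1.
- A 50% category of a four-category trait (3 df, critical value 7.815): sqrt(7.815 × 0.25/1500) = 3.61, and 3.61 + 2.53 = 6.14 points.

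The same non-significant p-value therefore carries a different bound for each trait.

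**Dependence on n.** Section 4.1 says "Five types of online sources will be used to reach young adults". Source sizes are not given. I take 1500/5 = 300 as an illustration; it is the most that the smallest source can have if each participant has one source. At n = 300 the non-centrality for a 5-point gap is 300 × 0.0025/0.25 = 3.0. The test then rejects 41% of the time and misses 59%, against 97% rejection at n = 1,500.

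**Precision of the alternative.** 95% half-width 1.96·sqrt(p(1−p)/n) at n = 1,500: 2.5 points for a 50% category and 1.1 for a 5% category. At the assumed n = 300: 5.7 and 2.5 points.

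**Chance of meeting a margin, if one is set.** Take 5 points purely as an illustration and require the whole 95% interval to lie inside it. The observed gap must then be below 5 − 2.53 = 2.47 points. For one 50% category at n = 1,500:
- True gap 0: P(|Z| < 2.47/1.29) = 94%.
- True gap 2: P(Z < 0.47/1.29) = 64%.
- True gap 3: P(Z < −0.53/1.29) = 34%.

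**The case against.** The strongest reply is that the plan never says a non-significant result will be taken as proof. It says that demographics will be compared, and Hypothesis 1 speaks only of potential generalizability. A reader might infer that the investigators intend to accept the null; the documents do not say so. The gap is that they give no other route to a conclusion either.

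Second, full-sample non-significance is fairly informative: a 5-point gap on a 50% trait would be caught 97% of the time. This stands, and it would be wrong to call the tests uninformative. But the bound appears only if the interval is computed, it differs by trait, and it does not help in reading a significant result.

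Third, a reader might infer that the demographics are left open. Largely they are not. Section 4.4.1 lists seven census-style items and Hypothesis 1 removes race/ethnicity, leaving six. Only a cross-reference and the categories are missing.

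Fourth, a reader might extend the criticism to the comparisons by source. They carry no hypothesis, and any figure for them rests on an assumed source size. They illustrate how the test depends on n and no more.

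Fifth, sections 13.1 and 13.2 promise no confidence intervals for any analysis, and percentages would ordinarily be tabulated. That is fair, but for most other hypotheses the predicted result is the alternative, whereas here it is the null. It is also true that, for a binary trait, the 95% interval covers zero essentially when chi-square is non-significant. The interval adds the size of the gap; it does not replace a criterion.

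**Conclusion.** The concern holds in this form: the planned tests can contradict the representativeness half of Hypothesis 1 but cannot in themselves support it, and no section supplies an estimate, interval or criterion that would. The logical point does not depend on any assumed number. Its size does: the 2.53-point threshold, the rejection rates and the bound of about 5 points are for a 50% binary trait at n = 1,500.

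The plan should be changed on this point, but the reach of the problem is limited. It touches a component of a primary aim and leaves the enrollment-rate test and the randomised comparisons as they are. The documents do not support the stronger claim that the sponsor will misread non-significance as proof.

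**What to change.** In section 13.1, Reach:

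1. Make the full-sample representativeness analysis the sample-minus-census difference with its 95% confidence interval, for each category of the section 4.4.1 demographics other than race/ethnicity. Cross-refer to that list and define the categories.
2. Keep the chi-square tests as descriptive, and state that a non-significant result will not be read as representativeness.
3. Report differences and intervals by recruitment source descriptively only, outside Hypothesis 1 and with no verdict.
4. If Hypothesis 1 is to be declared supported, prespecify and justify a margin. Otherwise state that this part of the hypothesis will be reported descriptively.

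The cost is wording and slightly more reporting, with no new data and no change in sample size. The real price attaches to item 4, because a margin-based verdict may fail. Under the illustrative 5-point margin, one 50% category with a true 2-point gap passes only 64% of the time, and the chance is lower if every category must pass. A uniform 5 points is also loose for small categories: a 5% category could lie anywhere from 0% to 10%. The choice of margin belongs to the sponsor.
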